Illuminating nerves, preserving function.™
Precision Surgery.™

[name]

**PHASE 1/2 TRIAL OF ALM-488 IN PATIENTS UNDERGOING
HEAD & NECK SURGERY**

PROTOCOL NUMBER: ALM-488-001

Product: ALM-488 Sterile Solution

Sponsor: Alume Biosciences, Inc.
[name]
[name]

Date of Protocol: 24 August 2020

Protocol Version	Issue Date
Original Protocol	26 April 2020
Amendment 1	24 August 2020

STUDY SUMMARY

Name of Sponsor	Alume Biosciences, Inc.
Name of Investigational Product	ALM-488 Sterile Solution
Name of Active Ingredient	ALM-488
Protocol Title	Phase 1/2 Trial Of ALM-488 In Patients Undergoing Head & Neck Surgery
Protocol Number	ALM-488-001
Phase of Development	Phase 1/2
Study Duration	18 months
Study Center(s)	Multi-center study (United States)
Objectives	
Primary Objective:
 
 To evaluate the safety of ALM-488 administered by intravenous (IV) infusion to patients undergoing head and neck surgery. 
Secondary Objectives:
 
 To characterize the pharmacokinetics (PK) of ALM-488 in patients undergoing head and neck surgery. To determine the recommended dose of ALM-488 needed to generate an adequate fluorescence signal in nerves. To evaluate the effect of timing of administration of ALM-488 relative to surgery (e.g., up to 5 hours before surgery) on adequacy of fluorescence nerve labeling.
Diagnosis and Main Inclusion/Exclusion Criteria	
This study will be conducted in patients who are undergoing head and neck surgery. Each subject must meet the following criteria to be enrolled in this study:
 
Inclusion:
 
 The subject has a neoplasm located in the head and neck including parotid neoplasm, thyroid neoplasm, squamous cell carcinoma or an unknown primary with metastases to the cervical lymph node(s) or is undergoing a neck dissection for head and neck neoplasm in an unknown location. The subject's primary surgical treatment is by parotidectomy (superficial or total) or thyroidectomy (unilateral or bilateral) or cervical neck dissection, respectively. The subject can understand and is willing to sign a written informed consent document. The subject is a ≥ 18 years of age. The subject has a life expectancy of at least 6 months. The subject has a total bilirubin within institution's normal laboratory limits. The subject has an aspartate aminotransferase (AST)/serum glutamic-oxaloacetic transaminase (SGOT) and alanine aminotransferase (ALT)/serum glutamic-pyruvic transaminase (SGPT) within institution's normal laboratory limits. The subject has adequate renal function, defined as glomerular

	
filtration rate (GFR) ≥ 60 mL/min/1.73 m².
 
 9. The subject, if of childbearing potential, must have a negative urine or serum pregnancy test and be using a medically acceptable form of contraception (e.g., hormonal birth control, intrauterine devices, double-barrier method) or abstinence. The subject, if male, must use a medically acceptable form of contraception (e.g. condom) or abstinence. 10. The subject is willing to remain on-site for approximately 23 hours after administration of ALM-488 or, if required, stay overnight after the surgical procedure. 11. The subject plans to undergo head and neck surgery. 
Exclusion:
 
 1. The subject has had prior radiation or chemotherapy for any prior head and neck neoplasm. 2. The subject has had open surgery in the ipsilateral head and neck within 1 year before administration of the investigational product (IP). 3. The subject has abnormal cardiac rhythm not controlled with medication, history of stroke within 1 year, history of coronary events within 1 year, and/or heart failure within 1 year before administration of the IP. 4. The subject has a history of drug-induced acute tubular necrosis. 5. The subject has current evidence of renal disease defined as glomerular filtration rate (GFR) < 60 mL/min/1.73 m². 6. The subject has received a systemic investigational drug of any kind for any indication within 6 weeks before administration of the IP. 7. The subject is pregnant or breastfeeding. 8. The subject has unresolved acute toxicity from prior anti-cancer therapy, as graded by the National Cancer Institute (NCI) Common Terminology Criteria for Adverse Events (CTCAE) v5.0. Alopecia, neuropathy \leq Grade 2, and other non-acute toxicities are acceptable. 9. The subject has a history of fluorescein allergy. 10. The subject has a history of severe or steroid dependent asthma. 11. Any other criteria deemed by the PI that may prevent the patient from successfully completing the trial.
--	--

## 1 Abbreviations

AE	Adverse Event
ATC	Anatomical Therapeutic Class
DLT	Dose Limiting Toxicity
ECG	Electrocardiogram
eCRF	Electronic Case Report Form
ENR	Enrolled analysis set
FAS	ALM-488 Activity Full Analysis Set
FL	Fluorescence
ICF	Informed consent form
IDMC	Independent Data Monitoring Committee
IRR	Infusion-related reaction
IV	Intravenous
MedDRA	Medical Dictionary for Regulatory Activities
NCI-CTCAE	National Cancer Institute – Common Terminology Criteria for Adverse events
PAS	PK Analysis Set
PK	Pharmacokinetics
PT	Preferred Term
RMANOVA	Repeated Measures Analysis of Variance
SAE	Serious Adverse Event
SAF	Safety Analysis Set
SAP	Statistical Analysis Plan
SOC	System Organ Class
SRC	Safety Review Committee
TEAE	Treatment Emergent Adverse Event
TLF	Tables, Listings, and Figures
WHO	World Health Organization
WLR	White Light Reflectance

QMS Document Name: Statistical Analysis Plan	Page 6 of 29
QMS No (include version ref): STF-015-GL.02	Document date: 09JUL2019
CONFIDENTIAL	

## 2 Introduction

### 2.1 Preface

The purpose of this document is to detail the statistical methodology to be used for the final statistical analysis of study ALM-488-001.

This Statistical Analysis Plan (SAP) covers the statistical summaries, analyses and methods of all the non-pharmacokinetic (PK) data. All details of the statistical summaries, analyses and methods for the PK data will be specified in a separate PK SAP. This SAP should be used in conjunction with the protocol. If there are any discrepancies between the protocol and SAP, this SAP will prevail. Any deviations from this SAP that are implemented in the final analysis will be documented with sound clinical and statistical rationale in the Clinical Study Report (CSR).

A separate document contains the table, listing and figure specifications and any example programming codes.

### 2.2 Timing of Statistical Analyses

- The following statistical analyses are planned for this study:
- Dose Escalation or De-Escalation
- Dose Timing Determination

## 3 Modification History

### 3.1 Changes to the Planned Analyses

The statistical analyses as specified in this SAP are mostly consistent with the statistical analyses as specified in the study protocol version Amendment 1, 24 August 2020.

We propose to include two additional specific analysis sets ENR, and DLT. They will allow to better describe the different steps of the study. They are not defined in the protocol. The additional analysis sets are defined below in section 5.

This SAP has been updated based on changes associated with protocol amendment 1.0.

## 4 Study Design

This is a Phase 1/2, open-label study in subjects undergoing head and neck surgery. The study will include up to 6 Dose Escalation/De-Escalation cohorts, followed by 2 pre-planned additional Dose Timing cohorts. Dose cohorts will start at 100 mg and follow the escalation/de-escalation described in the protocol.

Indication	Parotid Neoplasm, Thyroid Neoplasms, Head and Neck Neoplasms, Head and Neck Surgery
Design	Open-label study: Dose Escalation/Dose De-Escalation and Dose Timing cohorts

QMS Document Name: Statistical Analysis Plan	Page 7 of 29
QMS No (include version ref): STF-015-GL.02	Document date: 09JUL2019
CONFIDENTIAL	

Phases	Phase 1/2
Primary Objective	To evaluate the safety of ALM-488 administered by intravenous (IV) infusion to subjects undergoing head and neck surgery.
Secondary Objectives	
 
• To characterize the pharmacokinetics (PK) of ALM-488 in subjects undergoing head and neck surgery.
 
• To determine the recommended dose of ALM-488 needed to generate an adequate fluorescence signal in nerves.
 
• To evaluate the effect of timing of administration of ALM-488 relative to surgery (e.g., up to 5 hours before surgery) on adequacy of fluorescence nerve labeling.
 

Exploratory Efficacy Objectives	
 
• To evaluate the ability of imaging techniques (i.e. camera systems) to distinguish nerve tissue from non-nerve tissue.
 
• To evaluate the intensity of signal of fluorescence relative to nerve diameter.
 
• To evaluate the intensity of signal of fluorescence when there is overlying tissue.
 
• To assess the depth of fluorescence penetration when there is overlying non-nerve tissue.
 
• To evaluate surgeon confidence and operating time with a surgeon rating scale.
 

Treatment	ALM-488 Sterile Solution is an intravenously administered, synthetic, peptide dye conjugate indicated for the real-time intraoperative fluorescence detection and localization of nerve tissue.
Number of subjects	9-36 subjects in the Dose Escalation/De-Escalation cohorts 12 subjects in the Dose Timing Cohorts Total 21-48 subjects
Interim analysis	No formal interim analysis is planned for this study
Planned enrolment	Three sites in the United States.

The aim is to determine the lowest possible dose that achieves adequate imaging performance (nerve identification) with an acceptable toxicity profile. The Safety Review Committee (SRC) will determine the Optimal Dose based on 1) the safety data and 2) adequacy of fluorescence observed in each of the dose groups. Following determination of the Optimal Dose, Dose Timing Cohorts will

QMS Document Name: Statistical Analysis Plan	Page 8 of 29
QMS No (include version ref): STF-015-GL.02	Document date: 09JUL2019
CONFIDENTIAL	

commence at this Optimal Dose. The Dose Timing Cohorts will compare fluorescence characteristics at different ALM-488 administration times before surgery (3-5 hours, 1-3 hours).

Please refer to Section 5 of the protocol for full details on the study design.

#### **4.1 Sample Size Estimation**

The primary objective of this study is to evaluate the safety of ALM-488 administered by intravenous (IV) infusion to subjects undergoing head and neck surgery.

At each dose level, a cohort of 3 subjects will be enrolled for safety and tolerability evaluation. If there are no subjects with a DLT at a given dose level, new subjects will be enrolled at the next dose escalation level. If there are  $\geq 1$  subjects having any DLT, the enrollment to that specific dose and dose escalation will stop. New subjects will be enrolled at the next dose de-escalation level. There will be a minimum of 3 cohorts. Given that there will be 3-6 subjects for each dose level, 9-36 subjects will be needed for the dose escalation/de-escalation cohorts.

It is anticipated that the proposed dose range (100-1000mg) is expected to yield optimal imaging performance, with an initial starting dose of 100mg that has been selected based on supportive nonclinical testing. If the 100 mg dose is found to provide adequate fluorescence imaging of nerves, a dose de-escalation schedule will be followed to ensure that the lowest effective dose is determined. If imaging at starting first de-escalated dose (75 mg) becomes less adequate compared to 100mg as determined by the SRC, then imaging at dose escalation schedule will resume - beginning at 200mg. The Optimal Dose will be determined by the SRC as the lowest possible dose and toxicity profile that achieves adequate imaging performance of nerves using WLR combined with FL.

The Dose Timing Cohort will use the Optimal Dose as defined by the SRC following completion of the Dose Escalation/De-Escalation cohorts. Subjects in the Dose Timing phase will be administered ALM-488 at two planned operative times before surgery to assess the impact of timing of administration on fluorescence image quality. This phase will consist of 2 cohorts, 6 subjects/cohort: (1) dose administration 3-5 hours in advance of surgery, (2) dose administration 1-3 hours in advance of surgery. A total of 12 subjects will be needed for the Dose Timing phase.

In summary, 9-36 subjects may be enrolled into the dose escalation/dose de-escalation cohorts and 12 subjects may be enrolled into the dose timing cohort. A total of 21-48 subjects may be enrolled into this study.

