#### **4.2 Randomization, blinding and unblinding procedures**

No randomization, blinding or unblinding procedures are planned for this study.

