### **5 Analysis Sets and Cohorts**

Analysis Sets are described as follows:

- Enrolled analysis set (ENR) defined as all subjects who provided informed consent.
- Safety Analysis Set (SAF), defined as all subjects who received at least one dose of ALM-488

QMS Document Name: Statistical Analysis Plan	Page 9 of 29
QMS No (include version ref): STF-015-GL.02	Document date: 09JUL2019
CONFIDENTIAL	

- Dose-Limiting Toxicity (DLT) Evaluable Set, defined as subjects who receive ALM-488 and either 1) complete the safety follow-up through the DLT evaluation period (i.e., Day 15 ± 8) or 2) experiences a DLT at any time during the DLT evaluation period.
- Activity Analysis or Full Analysis Set (FAS), defined as all subjects in SAF who also received at least one evaluable image.
- Pharmacokinetics (PK) Analysis Set defined as all subjects who completed a PK blood sampling period without any major protocol violations which would render the data unreliable. The PK will be the primary analysis set for the pharmacokinetic analyses. PK of analyses will be fully described in the PK SAP.

SAF will be used for all safety analyses. FAS will be used for all efficacy analyses. The PK Analysis Set will be used for all PK analyses; ENR set will be the primary analysis set for disposition and listings. PP set will constitute the primary analysis set for early efficacy. DLT Evaluable Analysis Set will be used to assess the tolerability of ALM-488 in the dose escalation phase.

The Dose Escalation/De-Escalation cohort (Cohort A) consists of all dose escalation/de-escalation cohorts: Cohort A1, A2, A3, A4, A5, A6. In case of DLT rate = 0 or special FDA requests additional cohorts may be added to the tables.

The Dose Time Determination cohort (Cohort B) consists of: Cohort B1 - dose administration 3-5 hours in advance of surgery, and Cohort B2 - dose administration 1-3 hours in advance of surgery.

If not otherwise stated in the respective section, the statistical analyses will be performed for the following analysis sets:

Analyses	ENR	FAS	DLT	SAF	PK
Disposition	✓				
Demographics and baseline characteristics				✓	
Medical history				✓	
Exposure and compliance				✓	
Previous and concomitant therapies				✓	
Early Efficacy		✓			
Pharmacokinetic					✓
Safety				✓	
Dose-Limiting Toxicity			✓		
Listings		✓		✓	

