### **7.2 Secondary Endpoints**

The endpoints to characterize the PK of ALM-488 will be fully described in the PK SAP.

The endpoints to determine the dose of ALM-488 needed to generate an adequate fluorescence signal in nerves include the following:

- Timing of administration of ALM-488 relative to surgery

QMS Document Name: Statistical Analysis Plan	Page 11 of 29
QMS No (include version ref): STF-015-GL.02	Document date: 09JUL2019
CONFIDENTIAL	

- Dose
- Intensity (signal-to-background ratio- SBR)
- Surgeon rating scale

The endpoints to determine the dose of ALM-488 needed to generate an adequate fluorescence signal in nerves will be summarized for each of Cohorts A1-A6, as well as overall for Cohort A.

The endpoints to evaluate the effect of timing of administration of ALM-488 relative to surgery on adequacy of fluorescence nerve labeling include the following:

- Timing of administration of ALM-488 relative to surgery
- Time from injection to skin incision
- Intensity (SBR)
- Surgeon rating scale

The endpoints to evaluate the effect of timing of administration of ALM-488 relative to surgery on adequacy of fluorescence nerve labeling will be summarized for each of Cohorts B1 and B2, as well as overall for Cohort B.

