### **13.1 Timing, Dose, Size and Intensity**

The efficacy endpoints pertaining to timing of administration, dose, and intensity (signal-to-background ratio SBR), along with the surgeon rating scale will be assessed throughout enrollment into Cohorts A1-A6 to determine the final dose for use in Cohorts B1 and B2. These efficacy endpoints will also be used to evaluate the effect of timing of administration of ALM-488 by comparison of Cohort B1 and B2. The following analyses are planned for these efficacy endpoints:

- For each Cohort, SBR will be averaged to get a single mean ratio per patient; then a paired t-test or Wilcoxon signed rank test will be used, as appropriate, to compare SBR between FL and WLR.
- SBR will be also listed by cohort type, and surgery type and device for both FL with WLR.
- Image intensity ratios will also be analyzed with repeated measures analysis of variance (RMANOVA) with timing, image, method (FL /WLR), and device (Zeiss/OnLume) as the repeated factors in the model.
- SBR for FL and WLR measurements will be plotted. Values to the right of the line will indicate that there is improved visualization with FL images and values to the left of the line will indicate that there is improved visualization with WLR images(Equal performance of FL versus WLR will be indicated by dashed line (slope = 1)].
- To further assess timing, Cohorts B1 and B2 will be compared. Image ratios will be averaged to get a single mean ratio per patient; then an unpaired t-test or Wilcoxon rank sum test will be used, as appropriate, separately for FL and WLR.

Paired t-tests will be used unless markedly non-normal data is observed including bimodal or other severe assumption violations; minor skewness is robust to the paired t-test and RMANOVA assumptions. If extreme skewness with outliers, or bimodal distributions are observed, then a Wilcoxon signed rank test will be used instead of a paired t-test and RMANOVA will be performed on the ranked data.

Similarly, unpaired t-tests will be used unless markedly non-normal data is observed including bimodal or other severe assumption violations; minor skewness is robust to the unpaired t-test assumptions. If extreme skewness with outliers, or bimodal distributions are observed, then a Wilcoxon rank sum test will be used instead.

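### The timing cohorts meet at 3 hours and the only named between-patient timing test uses the cohort label, so the recorded injection-to-incision time enters no specified model

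*SAP*

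**What the plan says.** The cohort definition appears twice in the SAP with the same limits: in Section 4.1 as "1) dose administration 3-5 hours in advance of surgery, (2) dose administration 1-3 hours in advance of surgery" and in Section 5 as "Cohort B1 - dose administration 3-5 hours in advance of surgery, and Cohort B2 - dose administration 1-3 hours in advance of surgery". Neither place says to which cohort an interval of exactly 3 hours belongs. On size, Section 4.1 states: "A total of 12 subjects will be needed for the Dose Timing phase". On allocation, Section 4.2 states: "No randomization, blinding or unblinding procedures are planned for this study".

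Section 13.1 gives the between-cohort analysis: "To further assess timing, Cohorts B1 and B2 will be compared. Image ratios will be averaged to get a single mean ratio per patient". Those patient means are tested between the two cohorts with a two-sample t-test or its rank-based counterpart, once for FL and once for WLR. Tables 14.2.4.1 and 14.2.4.2 (Section 20.1) report it.

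The actual interval is not ignored:
- Section 7.2 lists "Time from injection to skin incision" as an endpoint of the timing objective, summarised for B1, B2 and Cohort B overall.
- Section 12 plots the intensity ratio against it (Figure 14.3.2).
- Section 10.5 describes dose and timing by cohort.

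Section 13.1 also plans an RMANOVA that names timing among its repeated factors. It does not say whether this means cohort or actual time.

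**The concern.** Timing up to 5 hours before surgery is a secondary objective. Under the label comparison, patients dosed 2 h 50 min and 3 h 10 min before surgery are contrasted with each other, while patients dosed at 1 h and at 3 h are pooled. If incision slips, a B2 patient can end up with an interval inside the B1 window. The available text has no rule for analysing that patient.

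With six patients per cohort the test can detect only large differences. If it also sets aside timing information that has been collected, a null result becomes more likely and could be reported as showing that timing does not matter. Allocation is not randomised, so the label has no randomisation-based protection that would justify leaving the measured interval out of every specified model.

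**Working it through.** **Inputs from the SAP.** Windows 3-5 h and 1-3 h (4.1, 5); six patients per cohort (4.1); two-sided tests with 95% confidence intervals (8.1), from which a 5% level is inferred. The documents give no SD, effect size, power or delay data for this comparison, so everything on those is assumed.

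**The plan's own counts.** 2 × 6 = 12; 3 × 3 = 9 and 6 × 6 = 36; 9 + 12 = 21 and 36 + 12 = 48. All agree with Section 4.1. There is no power figure to reproduce.

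**Sensitivity of 6 v 6.** From the noncentral t distribution, 80% power needs a difference of 1.80 SD. Power for a 1 SD difference is 35%.

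**Separation in actual time.** The windows alone allow a difference in mean time from 0 h (all at 3 h) to 4 h (all at 1 h v all at 5 h). If times are uniform within each window, the expected difference is 4 − 2 = 2.0 h. Its standard error is √(2 × 0.333/6) = 0.333 h, so the 95% range is about 1.35 to 2.65 h.

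**Information kept by the label.** For a linear effect, the efficiency of the label test relative to regression on time is the squared correlation of label with time, which is between-cohort variance / total variance. With uniform times:
- within-window variance = 2²/12 = 0.333
- between-cohort variance = (2.0/2)² = 1.0
- share kept = 1.0/1.333 = 75%, so 12 patients count as 12 × 0.75 = 9

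Other assumed distributions, without delay:

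| Times within window | Mean gap (h) | Kept | Lost |
|---|---|---|---|
| Towards the far ends | 2.67 | 93% | 7% |
| Mid-window | 2.00 | 90% | 10% |
| Near 3 h | 1.33 | 78% | 22% |
| Uniform | 2.00 | 75% | 25% |
| Very near 3 h | 0.67 | 58% | 42% |

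**Delay (assumed exponential with mean d, added to uniform times).** The probability that a B2 patient passes 3 h is (d/2)(1 − e^(−2/d)). With the same mean delay in both cohorts, the expected contrast stays at 2.0 h and the share kept is 1/(1.333 + d²). With delay in B2 only, the contrast is 2 − d.

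| Mean delay d (h) | B2 past 3 h | Kept, both delayed | Contrast, both delayed (h) | Contrast, B2 only (h) |
|---|---|---|---|---|
| 0.5 | 24-25% | 63% | 2.0 | 1.5 |
| 1 | 43% | 43% | 2.0 | 1.0 |
| 2 | 63% | 19% | 2.0 | 0 |

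**Power by simulation (20,000 trials per slope, uniform times, no delay, linear effect, residual SD 1).**

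| Slope (SD per h) | By label | By actual time |
|---|---|---|
| 0.5 | 32% | 43% |
| 0.75 | 57% | 74% |
| 1.0 | 77% | 92% |

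**A peak at 3 h.** Suppose the signal falls as (t − 3)². With uniform times the mean of (t − 3)² is 4/3 in both cohorts, so the B1 v B2 difference is zero. By symmetry the linear slope is zero too. Neither analysis would show the loss at 1 h and 5 h; only a curvature term or a plot could.

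**The case against.** The strongest reply is that planned window and actual interval answer different questions. Cohort membership is fixed by plan before incision, and comparing planned windows tells a site which window to schedule. The actual interval depends on later events, such as delay, that may relate to case complexity or site. This stands. It is a reason to keep B1 v B2 and to add the regression beside it, not in its place.

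Second, part of the remedy is already in place. The interval is summarised by cohort, the Section 8.1 default statistics include minimum, median and maximum, and the plot in Section 12 lets a reader see 12 patients directly. Deviation tables may capture out-of-window dosing. This also stands, but it yields no estimate with a confidence interval and no dedicated count of patients outside the window.

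Third, SAP Section 4 refers to protocol Section 5 for the full design, and that section is not in the text available here. A rule on windows may exist there.

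Three stronger readings are tempting and should be resisted:
- **Timing is compared only by label.** This is true of the named B1 v B2 test. But actual time is an endpoint, is summarised and plotted, and the meaning of the RMANOVA term is open.
- **Surgical delay erases the contrast.** Delay of equal mean in both cohorts leaves 2.0 h intact and only blurs the label. Under uniform times, erasure needs about 2 h more mean delay in B2 than in B1, and the documents give no delay data.
- **A quarter of the information is lost.** That figure belongs to uniform times and a linear effect. It is not a property of the plan.

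**Conclusion.** The point holds as a gap in the specified analysis. The windows share 3 hours and guarantee no minimum separation, the named between-patient test is by label, and no clearly defined model uses the recorded interval. Listing timing as a repeated factor does not fit a design in which each subject is in one timing cohort.

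For a linear effect without delay, the label costs about 25% of the timing information with uniform times and about 7% to 42% across the other distributions tried. That makes 12 patients worth roughly 11 down to 7. Delay raises the cost. The power gains shown depend on assumed slopes and illustrate direction and rough scale only. The planned comparison is not invalid; it is less precise than the collected data allow, in a 6 v 6 comparison that has little precision to spare.

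**What to change.** In SAP Section 13.1:
- Keep the B1 v B2 comparison by planned cohort.
- Add a prespecified regression of each patient's mean FL SBR on the actual interval in hours over all 12 Cohort B patients. Report the slope per hour with its 95% confidence interval, and a quadratic term or smooth plot for curvature.
- State that neither a null slope nor a null B1 v B2 result excludes a peak near 3 hours.
- Define timing in the RMANOVA as a between-subject term.

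In the tables, show for each timing cohort the achieved interval (minimum, median, maximum) and the number of patients outside the planned window. In Sections 4.1 and 5, reconcile the shared 3-hour limit so that the cohort definitions do not overlap. The dosing windows themselves are a clinical matter and no change to them is proposed.

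The cost is SAP wording, one extra analysis and one small table, with no new patients or data. The regression assumes a simple shape over 1-5 h and has little power to detect curvature with 12 patients. The actual interval may be related to case complexity or site, so the slope should be read as an association.
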